The dislocated prosthesis is usually managed by a simple, closed reduction maneuver under general anesthesia with or without muscle relaxation, resulting in open surgical reduction rarely being needed (9-11). Time from admission to actual reduction often includes various steps (incl. several patient transfers between emergency units, radiology departments, operating theaters) which causes an unnecessarily long period of pain for the patient. In 2015, a fast-track system was introduced at Hvidovre Hospital on a trial basis for patients highly suspected for THA/HA dislocation (12). This resulted in a significant decrease in the time from arrival to reduction and overall time of hospitalization, without resulting in more complications. The study was retrospective and did not measure how patients experienced the change in practice.

A fast-track system must be specially designed for the local departments, due to differences in the logistical options from hospital to hospital. The purpose of this study is to design a fast-track pathway for patients referred to the University Hospital of Southern Denmark, Esbjerg, with high probability of having a dislocated hip prosthesis with the primary aim to reduce the time from arrival to reduction and the total hospitalization time. Secondary aims are to

- investigate whether quicker prosthesis reduction influences on hip function and quality of life afterwards
- reduce the pain experience immediately and in the long term
- increase patient satisfaction

without changing the overall complication rate and readmission/mortality

Methods:

Trial design

The study is designed as a prospective observational cohort trial, adhering to the STROBE guidelines (13). The present protocol will be registered at clinicaltrials.org and submitted for publication in an international journal.

Setting

The study is conducted at the University Hospital of Southern Denmark, Esbjerg, as a collaboration between the Department of Orthopedics, Department of Anesthesiology, Department of Radiology, and Department of Emergency.

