The study is planned to start September 1st, 2024, and will continue for two years. During the first year, the admitted patients will follow the current standard treatment pathway. After September 1st, 2025, a newly developed treatment pathway will be adhered to, and for the rest of the protocol, this pathway is described as the Fast-track pathway, as the expectation is that treatment strategy will shorten time to reduction.

All patients admitted with a dislocated THA or HA will be included in the study without prior informed consent. The patients are – disregard of cognitive status – admitted with a complication that requires acute treatment. After the acute treatment (reduction of the dislocated prosthesis), the patients are informed about the study and encouraged to participate in the second part of the study (see outcome section).

Participants

Inclusion criteria: All adult patients admitted to the Department of Emergency Medicine (Dept. of EM), University Hospital of Southern Denmark, Esbjerg, for suspected dislocated hip prosthesis who fulfills the following

- age > 18 years
- a history of either a THA or a HA in combination with at least one of the following terms:
 - having sustained a sudden, incorrect movement or twist in the hip joint in either a bending, sitting or supine position leading to inability to stand or walk
 - misalignment of the concerned lower extremity (typically shortened, with inward/outward rotation)

Exclusion criteria: Patients with

- recurrent dislocations during the same hospital admission (already “in the house”)
- anticipated difficult airway by the attending anesthesiologist
- anticipated need for extended respiratory or hemodynamic monitoring by the attending anesthesiologist
- American Society of Anesthesiologists (ASA) score > 3
- Body Mass Index (BMI) > 40
- active drug abuse
- contraindication for Propofol or Esketamine

Intervention

Referred patients will follow either the standard pathway or a newly developed fast-track pathway, specifically designed with regard of the local logistics and structure at the Dept. of EM, University Hospital of Southern Denmark, Esbjerg.

Patient reported to the coordinating nurse at the Department of Emergency Medicine, fulfilling the inclusion criteria's, without violating exclusion criteria's	
Standard Pathway (September 2024 - August 2025)	Fast-track Pathway (September 2025 - August 2026)

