Every admitted patient will be included for evaluation of the primary and secondary outcomes (a-e + j-k) regardless of the patient's cognitive status. However, the remaining secondary outcomes (f-i) will require that the patient is able to understand the Danish language and cognitively able to answer the questions meaningfully. A dedicated project nurse will assist during the hospital admission if required. A patient can be included several times due to recurrent dislocations which will be accounted for during statistical analysis.

Outcome/variable time table

Pre-admission (recall past 14 days)	Hospital ad- mission (Day 0)	Day 1	Day 3	Day 7	Day 14	Day 30	Day 90	Day 180	Day 365
Patient-reported outcomes									
NRS	NRS	NRS	NRS	NRS	NRS	NRS			
HOOS					HOOS		HOOS	HOOS	HOOS
EQ-5D					EQ-5D		EQ-5D	EQ-5D	EQ-5D
	Satisfaction								
Registry/Patient file outcomes									
	Time to reduction								
	Time to discharge								
	Per-operative Complications								
	Post-operative complications								
						Re- admissions			
						Mortality	Mortality		
Patient variables									
	Age								
	Sex								
	ASA-score								
	BMI								
	Specific comorbidities								
Prosthesis variables									
	Primary operation date								
	No. of previous dislocations								
	Type of prosthesis (incl. liner type)								

Information acquired from patient files: Information regarding patient-related factors (age, sex, ASA-score, BMI, and specific comorbidities) and prosthesis-related factors (primary operation date, number of previous dislocations, and type of prosthesis), as well as information regarding

30-days readmission and mortality, and 90-days mortality will be acquired from the patient files after acquired patient consent. The patient- and prosthesis-related factors will be used to control for potential confounding. The acquired patient file information is dated from admission to 90 days post-admission. The prosthesis-related information is dated to the primary operation date. We will only access patient files from patients who accept to participate, therefore 120 patients.

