As the acute treatment has been performed when the patient is asked for consent, we apply for the use of the data acquired during the acute treatment of the patient, regardless of whether they choose to participate in the secondary part of the study regarding the patient-reported outcomes, in order to not prolong the study unnecessary. This includes the patient- and prosthesis-related factors, as this will be used to control for potential residual confounding.

Sample size

Study sample size are based on the primary outcome “Time from arrival at the emergency entrance to prosthesis reduction”, applying a formula for RCT studies with clinically superiority design (21). The null-hypothesis dictates no difference in time from arrival at the emergency entrance to prosthesis reduction for patients following the Standard Pathway or the Fast-Track Pathway.

$$N = 2 \times \left(\frac{z_{1-\alpha} + z_{1-\beta}}{\delta - \delta_0} \right)^2 \times s^2$$

N = no. of patients in each group

Alpha-value = 0,05 (5% risk of type-1 error)

Beta-value = 0,90 (10% risk of type-2 error)

Delta-value (estimated true value between the two groups) \approx 4 hours

Delta₀-value (estimated clinical acceptable difference between the two groups) \approx 3 hours

S-value (pooled standard deviation (SD) for both groups) \approx 2.5 hours

A review of 16 randomly selected patients that was admitted to the University of Southern Denmark, Esbjerg, with a dislocated THA from January 2018 to May 2022 revealed a mean time from arrival at the emergency entrance to prosthesis reduction at 6 hours (range 2.7 – 9.0 hours) with a standard deviation at 1.6 hours.

$$N = 2 \times \left(\frac{1,645 \times 1,28}{4 - 3} \right)^2 \times 2,5^2 \approx 53 \text{ patients in each group}$$

Based on a review of the surgical procedures performed during the period 01.02 – 31.08.2022, we expect to admit 5-6 patients per month with a dislocated THA or HA, and we expect an attendance rate of >90% based on the primary outcome. Therefore, we will include 53 patients + 15% ≈ 60 patients in each group, due to the risk that specific comorbidities will lead to exclusion from the Fast-Track pathway by the anesthetic staff. It is thus expected that a total of 120 patients will be adhered to one of the two treatment algorithms over the course of 24 months.

Blinding

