The patients are informed that consent gives the trial manager, sponsor and sponsor's representatives as well as any supervisory authority direct access to obtain information in the patient's medical record, etc., including electronic medical records, in order to see information about the subject's health, which is necessary as part of the implementation of the research project and for control purposes, including self-control, quality control and monitoring, which they are obliged to carry out.

Statistics

Mean values with standard deviation (SD) are given for normally distributed data, while median values with interquartile range (IQR) are given for skewed data. In case of normally distributed data, two-sample t-test is used. Mann-Whitney U-test is used to compare continuous nonparametric variables and chi-square test is used to compare categorical variables. STATA version 18 will be used for all statistical analyses.

Economy

The main investigator and initiator is [name], Ph.D., post.doc.

The study is conducted as a collaboration between the Department of Orthopedics, Department of Anesthesiology, Department of Radiology, and Department of Emergency Medicine, University Hospital of Southern Denmark, Esbjerg. There are no special economics involved in the study between the departments, as the study is carried out as a part of normal daily, acute activity.

Vestjysk Orthopedic Fund will be applied for covering expenses to hardware (computer, Ipad etc.)

The Region of Southern Denmark's Research Fund will be applied for covering salary to a dedicated study nurse.

Grants are administered via an account that is subject to public audit.

There are no conflicts of interest.

Ethics

Permission to store and handle data is obtained upon application to the Region of Southern Denmark's internal register (24/34681). The Danish Law of data protection is observed.

The regional ethics committee has been applied for permission to conduct the study under special circumstances as acute research without the possibility of obtaining informed consent from the

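### The recalled pre-admission NRS, HOOS and EQ-5D scores are missing from the confounder list, and the tests named cannot adjust for them or for the factors that are listed

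*Protocol*

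**What the plan says.** **What is collected.** The first column of the outcome/variable time table is headed "Pre-admission (recall past 14 days" and holds NRS, HOOS and EQ-5D. NRS is repeated from Day 0 to Day 30. HOOS and EQ-5D are repeated at Days 14, 90, 180 and 365. One secondary aim, at the end of the Background, is to "investigate whether quicker prosthesis reduction influences on hip function and quality of life afterwards".

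**What is adjusted for.** Under the paragraph on information from patient files, the protocol states: "The patient- and prosthesis-related factors will be used to control for potential confounding". The factors are "patient-related factors (age, sex, ASA-score, BMI, and specific comorbidities) and prosthesis-related factors (primary operation date, number of previous dislocations, and type of prosthesis". The last paragraph before Sample size repeats the intention. The pre-admission scores are not on the list. The time table files them under patient-reported outcomes, not under patient or prosthesis variables.

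**How groups are compared.** The Statistics section states: "In case of normally distributed data, two-sample t-test is used", and then "Mann-Whitney U-test is used to compare continuous nonparametric variables and chi-square test is used to compare categorical variables". It names no regression model, change score or covariate.

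**How groups are formed.** The Setting section allocates by date: "During the first year, the admitted patients will follow the current standard treatment pathway". The fast-track pathway applies from the second year.

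**The concern.** Asking about the period before admission by recall is sensible, because an acute dislocation allows no prospective baseline. The same instrument's pre-admission score is also the most direct measure the study has of prior hip status. The plan collects it without assigning it any role in the analysis.

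This matters more than in a randomised trial. The two years can differ in their mix of THA, HA and recurrent dislocators, and the Background itself describes the elective and fracture populations as clearly different. If prior hip function or quality of life differs between the years, an unadjusted comparison attributes part of that difference to the pathway.

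The protocol also does not fit together here. It promises control for confounding, and says that repeat inclusions of one patient will be accounted for, but the tests it names can do neither. What is at stake is the patient-reported outcomes f to h (NRS, HOOS, EQ-5D), which rest on a smaller group than the primary outcome.

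**Working it through.** The protocol gives no sample size, SD or correlation for the patient-reported comparison, so there is no figure of its own to reproduce. The stated sample size concerns time to reduction only.

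**Inputs from the protocol**
- Planned size: 60 per group (Sample size).
- Share unable to answer questionnaires because of dementia: up to 15 to 20% (Patient information).
- Responders per group: 60 × 0.85 = 51 to 60 × 0.80 = 48. This is an upper limit, since language, refusal and exclusions reduce it further.

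**Assumptions (not in the protocol)**
- rho, the correlation between pre-admission and follow-up score: 0.4 to 0.7.
- d, the systematic difference between years in prior status that the listed factors do not explain: 0.2 SD, with larger values for illustration.
- Equal SDs before and after, independent patients, and a two-sided 5% test.

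**1. Bias if follow-up scores are compared unadjusted:** about rho × d.
- rho 0.4: 0.4 × 0.2 = 0.08 SD.
- rho 0.7: 0.7 × 0.2 = 0.14 SD.

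**2. Effect on the test.** The standard error of a group difference is sqrt(2/n): sqrt(2/51) = 0.198 SD and sqrt(2/48) = 0.204 SD. With no true pathway effect, the rejection rate is 1 − Φ(1.96 − rho·d/SE) + Φ(−1.96 − rho·d/SE).

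| rho | d (SD) | bias (SD) | rejection rate, n = 48 to 51 |
|---|---|---|---|
| 0.4 | 0.2 | 0.08 | about 7% |
| 0.7 | 0.2 | 0.14 | about 11% |
| 0.5 | 0.3 | 0.15 | 11–12% |
| 0.7 | 0.5 | 0.35 | 40–42% |

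The last two rows show sensitivity to d. Nothing in the protocol indicates that shifts of that size will occur.

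**3. If change scores were tested instead.** The bias is (rho − 1) × d: −0.6 × 0.2 = −0.12 SD at rho 0.4 and −0.3 × 0.2 = −0.06 SD at rho 0.7. A change score uses the baseline but over-corrects, so it does not remove the problem.

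**4. Precision.** With the baseline as covariate, the residual variance is 1 − rho² of the unadjusted value.
- rho 0.4: 1 − 0.16 = 0.84, a 16% reduction, equivalent to 1/0.84 = 1.19 times the sample.
- rho 0.7: 1 − 0.49 = 0.51, a 49% reduction, equivalent to 1/0.51 = 1.96 times the sample.
- Difference detectable with 80% power at n = 51: 2.80 × 0.198 = 0.55 SD unadjusted. Adjusted, it is 0.55 × sqrt(0.84) = 0.51 SD to 0.55 × sqrt(0.51) = 0.40 SD (unrounded 0.555 used).

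The precision gain does not depend on any imbalance between the years.

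**The case against.** **The Statistics section may not be the whole analysis.** It is a short generic list that names no outcome, and the promised handling of confounders and repeat inclusions could not be done with it alone. A statistical analysis plan may supply a model. That is fair, and it rules out saying that the baseline will certainly go unused. It does not remove the mismatch inside the protocol: the confounder list is explicit and omits these scores, and the tests named cannot take any covariate.

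**A reader might infer that differences in prior hip status pass in full into the comparison.** The document does not support this. Prosthesis type and number of previous dislocations are on the list and would absorb part of such a difference once a method existed. Even unadjusted, the carry-over is rho × d, not d. Nor does the protocol say that raw follow-up scores are tested; change scores remain possible.

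**A reader might call chance imbalance a bias.** It is not. With 48 to 51 per group, a chance baseline difference has a standard error of about 0.2 SD, and the two-sample test already allows for that. The bias argument needs a systematic difference between years, which the protocol neither reports nor sizes.

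**One range of rho is applied to every instrument and visit.** This objection stands in part. NRS in the first days after an acute dislocation may correlate only weakly with recalled pain over the previous 14 days, so the gain there is probably smaller.

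**The baseline is obtained after treatment.** Patients are first approached after reduction, so the pathway could colour their recall, and adjusting for such a score can itself introduce bias. This is a real limit. It calls for showing both results, not for leaving the score unused.

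**Conclusion.** The point holds in limited form. The protocol collects a baseline for NRS, HOOS and EQ-5D, omits it from its confounder list, and names tests that can adjust neither for it nor for the factors that are listed. In a comparison of two calendar years, a systematic difference of 0.2 SD in prior status beyond the listed factors would bias an unadjusted follow-up comparison by 0.08 to 0.14 SD and raise the false-positive rate from 5% to about 7 to 11%. Adjustment would lower residual variance by 16 to 49% whether or not the years differ. These figures rest on assumed values of rho (0.4 to 0.7) and d (0.2 SD), not on anything in the protocol.

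It would go too far to conclude that the patient-reported results will be biased, or by how much, since the document contains no evidence of a shift between years. The primary outcome, time to reduction, has no pre-admission score and is not touched by this point. It should be corrected because it bears on a stated secondary aim and the data are already planned.

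**What to change.** - Add the recalled pre-admission score of the same instrument to the confounder list for outcomes f to h.
- For these outcomes, replace the two-sample tests with a linear mixed model containing pathway, visit, pathway-by-visit, the recalled pre-admission score, and the listed patient and prosthesis factors. Include a random effect or clustering for patients included more than once, in addition to the correlation between visits within an admission. ANCOVA at each time point would be acceptable only with the same allowance for repeat admissions.
- Report the adjusted mean difference with its 95% CI at each visit.
- As a sensitivity analysis, report the result without the recalled score, because that score is obtained after reduction.
- Reconcile the Statistics section with the confounder paragraph, so that the promised control has a named method.

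Patient satisfaction (outcome i) has no pre-admission value and lies outside this change.

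The cost is wording in the Statistics section and somewhat more analysis time. No further data are needed. The remaining limit is that a recalled score measures prior status with error, so adjustment reduces bias from prior status but may not remove all of it.

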Patient arrival through the ambulance entrance	Patient arrival through the ambulance entrance
Patient admitted to the Dept. of EM ward (Team 1 or 2), and transferred to a regular, standard patient bed	Patient is delivered directly to emergency trauma room no. 4 (located in conjunction of the ambulance entrance), and transferred to a radiolucent trauma bed
Patient is seen by the delegated nurse; vital parameters measured and registered, together with patient information	The orthopedic doctor AND the anesthesiologist on duty is notified and will arrive to the trauma room at their earliest convenience, depending on other acute activities
Patient is examined by one of three doctors on duty from the Dept. of Orthopedics, when	Patient is seen by the delegated nurse; vital parameters measured and registered, together with patient information, and X-ray is ordered

available (varying degree of education), and X-ray is ordered	
Patient is moved to the X-ray room (same floor level), (transfer to a special X-ray bearing is required) and will be returned to the bed ward	The diagnosis is verified by X-ray on site, by transportable X-ray machine, carried out by the radiology staff, without the need for patient transfer
Diagnosis is verified and the patient's medical files is updated	Patient's medical files is updated by the orthopedic doctor on duty (a standard paragraph will be developed for quick documentation in the medical records)
Patient is booked for a closed reduction maneuver in the operating theater during a short general anesthesia	The anesthesiologist on duty prepares for local sedation, following the sedation algorithm designed for this study, assisted by an anesthesiology nurse
Patient is reported to the anesthesiologists on duty for the purpose of planning and preparation for the anesthetic procedure	Closed reduction is completed, and control X-ray is conducted immediately on site, by transportable X-ray machine, carried out by the radiology staff, without the need for patient transfer
Patient is transferred to the operating theater, depending on other surgical activities and fasting time	Patient is transferred to the Dept. of EM ward

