Closed reduction is completed during a short general anesthesia, often with simultaneous muscle relaxation. Patient is transferred back and forth to a surgical bearing to confirm reduction, using a C-arm X-ray (not useful for documentation)	Patient is seen by a physiotherapist and mobilized with/without walking aids
Patient return to the Dept. of EM bed ward	Patient is discharged with/without a planned outpatient follow-up by a hip surgeon, depending on the specific patient case
Patient is moved to the X-ray room for a control X-ray (same floor level), (transfer to a special X-ray bearing is required) and will be returned to the bed ward	
Patient is seen by a physiotherapist and mobilized with/without walking aids	

Patient is discharged with/without a planned outpatient follow-up by a hip surgeon, depending on the specific patient case	
--	--

Assumed fast-track advantages includes

- elimination of several patient transfers back and forth from the Dept. of EM bed ward to X-ray rooms and operating theater (saves **time** and **hospital resources**)
- elimination of several patient transfers between different beds (reduces **patient pain** and **discomfort**)
- hip reduction in sedation rather than general anesthesia disregard of fasting time, - safely administered by anesthesiologists rather than by the orthopedic (saves **time**, increases **safety**)

Detailed description of standard anesthetic procedure for patients enrolled for standard pathway hip reduction (current practice)

Patients following the standard pathway and local guidelines, will receive a general anesthesia with a rapid sequence induction and intubation using Propofol 1-2 mg/kg, Alfentanil 0,2-0,3 mg/kg or Fentanyl 2-3 µg/kg and Suxamethonium 1 mg/kg. The patient is as a standard monitored with non-invasive blood pressure, saturation, pulse, 3-point ECG and end-tidal CO₂. More extensive monitoring may be used if considered necessary by the attending anesthesiologist.

Detailed description of new fast-track sedation procedure for patients enrolled for fast-track hip reduction

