The goal for the new fast-track sedation pathway is a short deep sedation, according to the definition of level of sedation by ASA (14). This is for optimal patient comfort and success and with very low risk of aspiration (15, 16). The patient is sedated with Propofol 0,5-1 mg/kg and/or Esketamine 0,1-0,5 mg/kg. If a repeat dose is necessary, it is with Propofol 0,2 mg/kg and/or Esketamine 0,1-0,5 mg/kg (17, 18). Before sedation an intravenous line is placed with 1 L Ringer Acetate and the patient will receive a nasal cannula with an oxygen flow of 2-5 L/min. During the sedation the patient is monitored with a non-invasive blood pressure, saturation, respiratory rate, pulse and 3-point ECG and the nurse anesthetist and anesthesiologist will continuously observe the depth of sedation and respiratory drive. After the hip reduction, the patient is observed and monitored until the sedation has worn off and there is no risk of airway obstruction.

Outcomes

The *primary* outcome is time from arrival at the emergency entrance to prosthesis reduction.

The *secondary* outcomes are:

- a) total hospitalization time from arrival to discharge
- b) intra-operative complications (fracture, unsuccessful reduction, aspiration, need for mask ventilation and/or intubation, others)
- c) post-operative complications (cardiac, pulmonal, thrombo-embolic events, nerve damage, re-dislocation, others) during hospitalization
- d) 30 days re-admission
- e) 30- and 90-days mortality
- f) hip-related pain measured by a 10-digit numeric rating scale (NRS)
- g) patient-reported outcome (PRO) using the Hip disability and Osteoarthritis Outcome Score (HOOS), domains ¹⁾PAIN, ²⁾OTHER SYMPTOMS, ³⁾FUNCTION IN DAILY LIVING, AND ⁴⁾HIP-RELATED QUALITY OF LIFE (19)
- h) Health-related quality of life using the EQ-5D questionnaire (20)
- i) patient satisfaction
- j) time consumption by the involved staff (orthopedic, anesthetic, radiology staff etc.)
- k) total hospital costs during admission

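### The factors named for confounder control are all patient and prosthesis factors; arrival period and weekday, obtainable from the arrival timestamp, would be worthwhile additions for an outcome that measures logistics

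*Protocol*

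**What the plan says.** The primary "outcome is time from arrival at the emergency entrance to prosthesis reduction" (Protocol, Outcomes). Patients are allocated by calendar period: standard pathway from September 2024 to August 2025, fast-track from September 2025 to August 2026 (Setting and Intervention).

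The paragraph on information acquired from patient files lists, for the patient, sex, age, BMI, ASA score and comorbidities. For the prosthesis it lists type, date of the primary operation and count of earlier dislocations. It then states: "The patient- and prosthesis-related factors will be used to control for potential confounding". The paragraph just before Sample size repeats this purpose for the same two groups of factors. The outcome/variable time table shows no hour or day of arrival.

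The Intervention table describes what the wait depends on:

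- Standard pathway: an orthopedic doctor examines the patient once one is free, and transfer to theatre happens "depending on other surgical activities and fasting time".
- Fast-track pathway: the two doctors on duty "will arrive to the trauma room at their earliest convenience, depending on other acute activities".

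Among the assumed advantages of fast-track the protocol lists "hip reduction in sedation rather than general anesthesia disregard of fasting time". The Statistics section names the two-sample t-test, the Mann-Whitney test and the chi-square test, and no regression model.

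**The concern.** The named covariates describe the patient and the implant, whereas the outcome measures how fast a hospital process runs. By the protocol's own account, the wait in both pathways depends on how busy the staff are and, in the standard pathway, on theatre load and fasting. In acute care these commonly vary between day and night and between weekdays and weekends. Adjusting for every listed factor would leave that variation untouched.

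Two things are at stake. First, the comparison is not randomised, so a real change in the share of night or weekend arrivals between the years would enter the estimated saving. Second, even with the same mix in both years, predictable variation stays in the error term and the interval is wider than it need be. Total hospitalization time may be affected too, since discharge follows physiotherapy and stays are typically 12-24 hours.

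**Working it through.** The protocol gives no figure for the effect of arrival hour or weekday, so there is none to reproduce. The check asks how much adjustment could matter.

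**Inputs from the protocol (Sample size).** 60 patients per group; planning SD 2.5 h; SD 1.6 h in the review of 16 earlier patients; expected difference 4 h; margin 3 h.

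**Assumptions.** Share of out-of-hours arrivals p = 0.5; out-of-hours arrivals wait D hours longer, the same in both pathways.

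**1. Unadjusted standard error of the difference**, SD × √(2/60):

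- SD 2.5 h: 2.5 × 0.1826 = 0.46 h (95% half-width 1.96 × 0.456 = 0.89 h).
- SD 1.6 h: 1.6 × 0.1826 = 0.29 h (half-width 1.96 × 0.292 = 0.57 h).

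**2. Precision gain for a given share of variance explained.** The SE is multiplied by √(1 − R²); the equivalent gain in patients is 1/(1 − R²) − 1.

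- R² = 0.10: √0.90 = 0.949, so the SE is 5% lower; 1/0.90 − 1 = 11% more patients.
- R² = 0.30: √0.70 = 0.837, so the SE is 16% lower; 1/0.70 − 1 = 43% more patients.

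At the planning SD, the SE of 0.46 h would become 0.43 h or 0.38 h.

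**3. Delay that corresponds to that R²**, R² = D² × p(1 − p) / SD²:

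| D | R² at SD 1.6 h | R² at SD 2.5 h |
|---|---|---|
| 1.0 h | 0.25/2.56 = 0.10 | 0.25/6.25 = 0.04 |
| 1.75 h | 0.766/2.56 = 0.30 | 0.766/6.25 = 0.12 |
| 3.0 h | 2.25/2.56 = 0.88 | 2.25/6.25 = 0.36 |

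So 10-30% matches a delay of about 1.0-1.75 h at the SD of 1.6 h. If the true SD is 2.5 h, the same delays explain only 4-12%, and the SE falls by about 2-6%. A 3 h delay would take up 88% of the variance seen in the earlier patients, so it fits the protocol's own data poorly.

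**4. Chance imbalance.** The SE of the between-year difference in the out-of-hours share is √(2 × 0.25/60) = 0.091, or 9.1 points. With D = 1.0-1.75 h this moves the estimate by 0.09-0.16 h. That equals √R² × SE at the SD of 1.6 h (0.31 × 0.29 = 0.09; 0.55 × 0.29 = 0.16). It is therefore a part of the standard error in step 1 and not an addition to it.

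**5. Systematic shift.** Bias is D × change in share. A true change of 10 or 20 points (assumption) with D = 1.0-1.75 h gives 0.10-0.18 h or 0.20-0.35 h. To use up the 1 h between the expected difference and the margin, the share would have to change by 1/1.75 = 57 points or more.

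**The case against.** A reader might infer that arrival time is the main driver of the wait, that the trial measures it, and that leaving it out biases the primary comparison. The protocol does not support this. It ranks no drivers, mentions neither hour nor weekday, and does not list either as a variable. The link from workload and fasting to hour and weekday is a clinical inference, though an ordinary one. A predictor confounds only if its distribution differs between the groups. Here the groups are two full September-August years at one department under one inclusion rule, and nothing in the text suggests a different arrival mix. Chance imbalance is sampling error already in the unadjusted interval; to call it bias and also count it as lost precision would count it twice.

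Other objections have some weight. The protocol does not say that only the listed factors will be used, and a fuller covariate list may stand in an analysis plan that was not at hand. The delay may also be smaller under fast-track, which avoids the theatre and the fasting wait: a 4 h saving from a 6 h mean leaves about 2 h in total. The gain would then be smaller than calculated.

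The core of the point remains. The protocol names the factors it will use, and none represents the operational influences it describes. The precision argument needs no imbalance between the years, and arrival time has to be recorded anyway.

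**Conclusion.** The point holds as a cheap improvement to the adjustment set, not as a demonstrated bias. Arrival period and weekday versus weekend or holiday are plausible strong predictors of both time outcomes, precede treatment and need no new data. Including them guards against any shift in arrival mix between the two years and lowers the SE by about 5-16% if they explain 10-30% of the variance. That range assumes half of arrivals out of hours, an SD of 1.6 h and a common delay of about 1.0-1.75 h; at an SD of 2.5 h the same delays give about 2-6%. Against an expected 4 h difference, even a systematic 20-point shift would move the estimate by only 0.20-0.35 h under these assumptions.

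**What to change.** In the Outcomes section, where the confounding factors are listed and again in the paragraph before Sample size, add arrival period (day, evening, night) and weekday versus weekend or holiday. Derive both from the arrival timestamp, and apply them to time to reduction and total hospitalization time.

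An addition to the list is not enough, because the tests under Statistics cannot take covariates. Name there an adjusted regression model with pathway plus these and the already listed covariates, for example linear regression in hours, which keeps the result on the scale used for the sample size.

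Do not adjust for the fasting delay itself. The fast-track pathway is meant to remove it, so adjusting for it would remove part of the effect under study. Arrival hour and weekday do not have this problem.

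The cost is a few sentences, three model terms (two if arrival period is reduced to in-hours and out-of-hours) and a little more analysis work, with no extra patients or data collection.
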